3.1.4.15 EuroQoL 5-dimension, 5-level (EQ-5D-5L) score

The EQ-5D-5L descriptive system comprises the following 5 dimensions, each describing a different aspect of health: mobility, self-care, usual activities, pain/discomfort, and anxiety/depression. Each dimension has 5 response levels of severity: no problems, slight problems, moderate problems, severe problems, 'unable to' /extreme problems. In addition, the EQ-VAS records the overall current health on a vertical visual analogue scale, where the anchors are labelled 'the best health you can imagine' and 'the worst health you can imagine'.

3.1.4.16 PGIS

Participants will be asked a single question to rate their severity of CRS-related symptoms over the past 7 days

3.1.4.17 PGIC

The PGIC is a self-assessment of the participant's overall change in CRS-related symptom severity compared to pretreatment.

3.1.4.18 Medical Outcomes Study Sleep Scale (MOS Sleep-R) score

MOS Sleep-R is a 12-item instrument with a 4-week recall designed to measure key aspects of sleep, such as disturbance, adequacy, somnolence, and quantity. The score ranges from 0 to 100, lower scores indicating better sleep and higher scores indicating worse sleep. The scale yields a sleep problem index and scores on the following 6 subscales: sleep disturbance, snoring, shortness of breath or headache, sleep adequacy, sleep somnolence, and sleep quantity.

3.1.4.19 Work Productivity and Activity Impairment-Specific Health Problem (WPAI-SHP)

The WPAI-SHP is a questionnaire to measure the effect of a specific health problem on the participant's work productivity and normal daily activities. Employed participants report absenteeism (time absent from work), and presenteeism (time at work but not fully productive), which are calculated to a work productivity index. All participants report time away from normal activities.

3.1.5 Summary Statistics

Categorical data will generally be summarized with counts and percentages of subjects. Percentages by categories will be based on the number of subjects with no missing data, i.e. the percentages for the non-missing categories will add up to 100%. Quantitative data will generally be summarized with descriptive statistics including n (number of non-missing values), mean, median, standard deviation, interquartile range (Q1, Q3) and range (minimum, and maximum).

3.1.6 Hypothesis Testing

For the primary efficacy endpoint, the null and alternative hypotheses to be tested are:

$$H_0: \mu_L = \mu_C$$

vs

$$H_1: \mu_L \neq \mu_C$$

where μ_L and μ_C are true mean CFBL in 3CS at Week 24 for participants receiving the LYR-210 (7500 μ g) treatment and the control (sham) treatment, respectively.

Unless otherwise specified, all hypothesis tests will be conducted at a 2-sided significance level of 0.05. Two-sided equal tailed 95% (asymptotic) confidence intervals (CIs) will also be calculated.

[figure not shown]
3.1.7 Multiplicity

As described in Section 2.3.2, a fixed sequential testing procedure will be implemented. In a hierarchical step-down manner, the primary efficacy endpoint will be tested at the 2-sided 0.05 level first, followed by testing the prespecified key secondary endpoints, each at a 2-sided significance level of 0.05, in the order specified in Section 2.3.2. Inferential conclusions

about these efficacy endpoints will require statistical significance of the previous key secondary endpoints and the primary efficacy endpoint.

With this method, statistical significance cannot be achieved for a key secondary endpoint unless statistical significance is achieved for all key secondary endpoints already tested. This approach ensures that the overall study-wise type-1 error rate is controlled at 0.05 for the comparisons between treatment and control on the primary and all 4 key secondary endpoints.

Figure 2. Multiplicity

3.1.8 Handling of Dropouts and Missing Data

3.1.8.1 Handling of Partial or Missing Dates for Prior and Concomitant Medications

The goal for imputing a partially missing date is to select the most conservative date within the possible range specified by the non-missing data. The imputation rules in Table 3 will be used unless otherwise specified.

Table 3. Imputation Rules for Missing Date

Date	Type of Missing Date	Handling of Missing Date
Event Start Date (e.g., YYYY-MM-DD)	Completely missing	No imputation will be applied.
	Only YYYY is available	Use the first day of YYYY to impute the missing month and date parts of the start date.

Event End Date (e.g., YYYY-MM-DD)	YYYY and MM are available, but DD is missing	Use the first day of MM to impute the missing date part of the start date.
	Completely missing	No imputation will be applied. The event will be considered ongoing at the end of study.
	Only YYYY is available	Use the last day of YYYY to impute the missing month and date parts of the end date
	YYYY and MM are available, but DD is missing	Use the last day of MM to impute the missing date part of the end date

In the case where the imputed start date is later than the reported stop date, the imputed date will be set equal to the stop date.

In all listings, missing or partial dates will be left as they have been recorded.

3.1.8.2 Algorithm for Treatment Emergent Adverse Events (TEAE)

TEAE is defined in Section 3.6.1.

For deriving the TEAE flag the following process of temporary date imputation is done for adverse event (AE) start date. The date imputation algorithm for incomplete adverse event start dates is described in Table . Classification of adverse event (TEAE or not) is then done using the imputed date.

In the following table, all dates are presented using an YYYY-MM-DD format. As an example, suppose First IMP administration = 2022-08-11 and several AEs have incomplete start dates.

Table 4. Imputation Rules for Missing AE start Date

Description of incomplete date	Imputed numeric date	Example	
		Character date	Imputed date
Day is missing			
YYYY-MM < YYYY-MM of [First IMP admin.]	YYYY-MM-01	2022-07-XX	2022-07-01
YYYY-MM = YYYY-MM of [First IMP admin.]	Min ([First IMP admin.], AE end date)	2022-08-XX	Min (2022-08-11, AE end date)
YYYY-MM > YYYY-MM of [First IMP admin.]	YYYY-MM-01	2022-09-XX	2022-09-01
Day and month are missing			
YYYY < YYYY OF [First IMP admin.]	YYYY-01-01	2021-XX-XX	2021-01-01
YYYY = YYYY OF [First IMP admin.]	Min ([First IMP admin.], AE end date)	2022-XX-XX	Min (2022-08-11, AE end date)
YYYY > YYYY OF [First IMP admin.]	YYYY-01-01	2023-XX-XX	2023-01-01
Day, month, and year are missing			

XXXX-XX-XX	Min ([First IMP admin.], AE end date)		Min (2022-08-11, AE end date)
------------	---------------------------------------	--	-------------------------------

YYYY = non-missing year, MM = non-missing month, DD = non-missing day, XX = missing field.

Actual data values as they appear in the original eCRFs will be presented in the data listings.

3.1.8.3 Missing data

All efforts will be made to minimize missing data. Participants who discontinued treatment early are encouraged to continue completing ePRO assessments through Week 24. Data collected after treatment discontinuation will be included in the analysis. For participants who undergo rescue treatment (SCS and/or sinonasal surgery for any reason), data collected post rescue treatment will be censored and imputed using the participant's worst possible.

3.2 Analysis Sets

3.2.1 Safety Analysis Set

Safety analysis set: all randomized participants who successfully received the study treatment (LYR-210 or control) on Day 1. Participants will be analyzed according to the treatment received. This is the primary analysis set for assessment of safety.

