7.1 Adverse events and treatment-emergent adverse events

An AE is any untoward medical occurrence (signs, symptoms, abnormal laboratory findings) in a participant regardless of relationship to the investigational product or procedure. Each AE is either expected or unexpected as described below. The site is required to report Aes that occur during the study. These events shall also be classified according to the suspected causality by the study investigator.

Throughout the course of the study, all efforts will be made to remain alert to possible Aes or untoward findings. If AEs occur, the first concern will be the safety and welfare of the participant. Appropriate medical intervention will be undertaken. Any AE observed by the investigator or reported by the participants, whether or not ascribed to the investigational procedure or product, will be recorded on the participant's AE case report form (CRF). A new AE CRF will be used for each AE. All on-going AEs that result in early termination (ET) from the study or are deemed to be study product- or procedure-related by the site investigator will be followed until resolution or stabilization of the AE.

Documentation regarding the AE should be made as to the nature, date of onset, end date, severity, and relationship to study product, action(s) taken, seriousness, and outcome of any sign or symptom observed by the physician or reported by the participant upon indirect questioning.

A treatment emergent AE (TEAE) is an AE that occurs or worsens on or after initiation of the LYR-210 administration/sham procedure.

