9.3.1 Analysis sets

- Safety analysis set: all randomized participants who successfully received the study treatment (LYR-210 or control) on Day 1. Participants will be analyzed according to the treatment received. This is the primary analysis set for assessment of safety.
- Intention-to-treat (ITT) analysis set: all randomized participants who successfully received the study treatment (LYR-210 or control) on Day 1. This is the primary analysis set for assessment of efficacy. Participants will be analyzed according to the treatment they were assigned to at randomization.
- Per-protocol (PP) analysis set: all randomized participants who successfully received the study treatment on Day 1, have post-Day 1 efficacy assessments, and are without any matrix dislodgement before Week 13 or important protocol deviations that might affect the accuracy and/or reliability of efficacy assessments.
- Pharmacokinetic (PK) analysis set: the approximately 30 randomized participants who successfully received the study treatment on Day 1 and have specific post-Day 1 PK assessments.

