3.2.2 Intent-to-Treat (ITT) Analysis Set

ITT analysis set: all randomized participants who successfully received the study treatment (LYR-210 or control) on Day 1. This is the primary analysis set for assessment of efficacy. The primary analysis will be conducted for ITT Analysis Set without nasal polyp while the remaining efficacy analyses will be conducted for ITT Analysis Set. Participants will be analyzed according to the treatment they were assigned to at randomization.

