3.6 Safety Analysis

Safety data will be summarized on the Safety Analysis Set.

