3.6.1 Adverse Events (AEs)

An AE is any untoward medical occurrence (signs, symptoms, abnormal laboratory findings) in a participant regardless of relationship to the investigational product or procedure. Adverse events that occur prior to the insertion of the study treatment in the extension period will be included in this period summary.

All AEs will be coded to primary system organ class and preferred term using MedDRA version 24.1 (or later version).

Treatment emergent adverse events (TEAEs) are defined as AEs that start during or after the implantation procedure of study drug or sham procedure but no later than 31 days (>31 days) after discontinuation of study treatment.

An overview of AEs will be provided including counts and percentages of subjects (and event counts) with the following:

- Any TEAEs (overall and by maximum severity)
- Any study product related TEAEs (overall and by maximum severity)
- Any study procedure related TEAEs (overall and by maximum severity)
- Any serious AEs (SAEs)
- Any treatment-emergent serious AEs (TESAEs)
- Any TEAEs leading to discontinuation of study product
- Any TEAEs leading to discontinuation of study procedure
- Any AEs leading to death
- Any TEAEs related to COVID-19

Counts and percentages of subjects (and event counts) will also be presented by primary system organ class and preferred term for each of the categories in the overview. Listings will be presented specifically for SAEs and TEAEs leading to discontinuation of study product.

Adverse events of Special Interests (AESI) and TEAEs leading to Discontinuation

Certain treatment emergent adverse events will be designated as AESI. These categories are:

- Ocular safety adverse events
 - Cataract: Preferred Terms of Cataract, cataract cortical, cataract subcapsular, cataract nuclear

- Increase in IOP: Preferred Terms of Intra ocular pressure increased, Ocular hypertension
- Glaucoma: Preferred Terms of Glaucoma, Open angle glaucoma, Angle closure glaucoma
- Nasal mucosal safety adverse events
 - Mucosal injury: Preferred Terms of Nasal mucosal disorder, Nasal mucosal erosion, Nasal septum ulceration, Nasal septum perforation, Nasal mucosal erythema, Nasal mucosal ulceration
 - Epistaxis: Preferred Term of Epistaxis.

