The number and percentage of participants reporting each category of AESI will be summarized by each treatment group. Difference and odds ratio in proportion of participants between the treatment groups will be calculated with its 95% confidence intervals.

Additionally, the difference and odds ratio in proportion of participants between the treatment groups and its 95% CI for the percentage of subjects with TEAEs leading to discontinuation of study treatment will be calculated.

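### The safety set omits participants whose Day 1 procedure was started but failed, although their adverse events are treatment-emergent by definition; the ITT set has the same success condition and is a modified ITT

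*SAP*

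**What the plan says.** **Analysis sets.** SAP 3.2.1: "Safety analysis set: all randomized participants who successfully received the study treatment (LYR-210 or control) on Day 1". SAP 3.2.2: "ITT analysis set: all randomized participants who successfully received the study treatment (LYR-210 or control) on Day 1". Protocol 9.3.1 has the same conditions: "Intention-to-treat (ITT) analysis set: all randomized participants who successfully received the study treatment (LYR-210 or control) on Day 1". The two sets differ only in analysis by treatment received or by treatment assigned. The per-protocol and PK sets also require success.

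**Failures.** Randomization comes before any treatment, and the treating investigator is unblinded (Protocol 3.5.4). Under Protocol 3.5.5, a participant in whom bilateral LYR-210 placement or the sham procedure cannot be completed is a treatment administration failure. Any matrix already placed is removed, a telephone contact at 7 (±2) days covers AEs and concomitant medication, and the participant may be replaced.

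**Adverse events.** Protocol 7.1: "A treatment emergent AE (TEAE) is an AE that occurs or worsens on or after initiation of the LYR-210 administration/sham procedure". SAP 3.6.1 counts "AEs that start during or after the implantation procedure of study drug or sham procedure", up to a limit of 31 days after treatment ends. Neither definition requires success. SAP 3.6: "Safety data will be summarized on the Safety Analysis Set". SAP 3.6.1 also plans a row for "Any TEAEs leading to discontinuation of study procedure", and for AESIs: "Difference and odds ratio in proportion of participants between the treatment groups will be calculated with its 95% confidence intervals".

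**All randomized participants** appear in the disposition summary (Protocol 9.3.4, SAP 3.3.1) and in the Day 1 procedure summary (SAP 3.3.9), which records whether bilateral insertion succeeded. The SAP 3.3.3 table of analysis sets is based on the ITT set.

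**The concern.** A participant in a failed attempt has had local anesthetic and endoscopy, and may have had a matrix placed and removed. The AESI categories include epistaxis and mucosal injury, which such an attempt could plausibly cause. The plan collects these events and classes them as treatment-emergent, then leaves the participants out of the tables that describe the harm of the procedure. In particular, an AE that stops the Day 1 placement takes the participant out of the set, so it cannot appear in the row for TEAEs that led to stopping the procedure.

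On efficacy, success is known only after randomization and is determined by someone who knows the arm. Placing a matrix and performing a sham are different tasks, so failure could differ between arms. The primary comparison is then not strictly of the groups as randomized, and none of the analyses in SAP 3.4.1.2 and 3.4.1.3 shows whether that matters.

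**Working it through.** **Step 1. Follow one participant through the rules.** Take an AE that begins during LYR-210 placement and stops it.
- TEAE by Protocol 7.1 and SAP 3.6.1: yes.
- Collected (Protocol 3.5.5 and 7.6): yes.
- In the safety set (SAP 3.2.1): no, because treatment was not successfully received.
- In any TEAE or AESI summary (SAP 3.6): no.
- Counted as a failure in disposition and in the Day 1 procedure summary: yes, but without the AE.

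**Step 2. Reproduce the plan's figure.** From SAP 2.2.4: 100 LYR-210, 50 control, difference 1.31, effect size 0.63, two-sided alpha 0.05.
- SD = 1.31/0.63 = 2.079.
- SE = 2.079 × √(1/100 + 1/50) = 0.360.
- Power (noncentral t, 148 df) = 0.951, against the stated 0.95. It reproduces.

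**Step 3. Size for safety.** The documents give no failure rate and no AE rate in failures, so these inputs are assumptions: 120 LYR-210 attempts, k failures, an AESI tabulated at 10% in the current set, and a rate q in failures.

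Rate among all attempts = ((120 − k) × 0.10 + k × q)/120

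| k | q = 0 | q = 10% | q = 50% | q = 100% |
|---|---|---|---|---|
| 2 | 11.8/120 = 9.8% | 10.0% | 10.7% | 13.8/120 = 11.5% |
| 6 | 11.4/120 = 9.5% | 10.0% | 12.0% | 17.4/120 = 14.5% |

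For AEs that stop the Day 1 procedure, one in 120 attempts is 0.8% (exact 95% CI 0.02 to 4.6). The safety set would show none of these among 119 participants. Events at other procedures would be additional to this count.

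**Step 4. Size for efficacy.** Let a fraction fL of LYR-210 and fS of sham participants fail, with outcomes δ points worse, and let there be no treatment effect.
- Bias = (fL − fS) × δ.
- SE = 2.079 × √(1/(100(1 − fL)) + 1/(50(1 − fS))).
- Type I error comes from the noncentral t with noncentrality bias/SE.

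| fL | fS | Bias, δ = 1 / 2 | SE | Type I error, δ = 1 / 2 |
|---|---|---|---|---|
| 2% | 0 | 0.02 / 0.04 | 0.361 | 0.0503 / 0.0514 |
| 5% | 2.5% | 0.025 / 0.05 | 0.366 | 0.0505 / 0.0521 |
| 5% | 0 | 0.05 / 0.10 | 0.363 | 0.0521 / 0.0586 |
| 10% | 0 | 0.10 / 0.20 | 0.367 | 0.0584 / 0.0842 |

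If failures are equally frequent and alike in both arms, the bias is zero. If failures do better than others, its sign reverses.

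**The case against.** **A definition of an event is not a definition of a set.** A TEAE definition classifies events and an analysis set selects participants, so both can stand together. This is correct. A reader might infer that the SAP contradicts itself or that the events are lost. Neither follows: AEs are collected from consent (Protocol 7.6), SAEs are reported within 24 hours (Protocol 7.7.1), and individual data are listed (Protocol 9.3.2). What remains is a gap in the summaries.

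**The discontinuation row is not empty by construction.** A reader might infer that it can only be zero. It does not name the Day 1 procedure, and removal at Week 20 is also a procedure (Protocol 3.5.7). Only AEs that stop the Day 1 placement are barred from it.

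**All randomized participants are used somewhere.** They are, in disposition and in the Day 1 procedure summary. The statement is true only of efficacy and AE analyses.

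**The direction is unknown.** Failures have only about 7 days of specified follow-up, so slower events such as cataract or raised IOP could be recorded less often in them. Adding failures to the denominator could lower a rate, as the q = 0 column shows. The fix has to deal with this.

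**Failures should be few, and the efficacy set is openly defined.** Exclusion criteria 2, 8a and 9a screen out anatomy that would prevent placement, and both documents define the set identically. This limits the efficacy point to a matter of label plus one missing sensitivity analysis. It does not answer the safety point, since a single stopped procedure is worth showing.

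**Conclusion.** The point holds as a gap in the safety summaries and a mislabelled efficacy set. The safety part rests on the wording of the definitions and needs no assumed rate. Its size cannot be computed from the documents. Under the assumptions in the working, the AESI rate among all attempts moves from 10% to between 9.8% and 11.5% with 2 failures in 120, and to between 9.5% and 14.5% with 6.

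The efficacy part is minor. Type I error stays at about 0.050 to 0.052 with 2% failures, or with 5% if sham fails half as often. A reader might take 0.084 as the expected inflation, but that needs 10% failures in the LYR-210 arm only, each 2 points worse, and nothing in the documents supports that combination.

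One smaller conflict should be settled at the same time. SAP 3.3.3 bases the analysis-set table on ITT, so it cannot show exclusions from ITT, whereas Protocol 9.3.4 reports set assignment for all randomized participants. SAP 3.3.1 partly covers this, because it counts successful Day 1 treatment with randomized participants as the denominator.

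**What to change.** 1. **Safety set.** In Protocol 9.3.1 and SAP 3.2.1, define it as all randomized participants in whom the LYR-210 or sham procedure was started, analysed by the procedure attempted. Because failures have only about 7 days of specified follow-up, tabulate Day 1 procedure-period AEs separately for all attempts. Show later-onset AEs with and without failures, or by exposure.
2. **Efficacy set.** Rename the current ITT set 'modified ITT' in both documents and keep it as primary. Add one prespecified sensitivity analysis of the primary endpoint in all randomized participants without polyps. State the imputation rule for failures without 3CS data, for example sham-based imputation with the tipping-point shifts of SAP 3.4.1.2. A rule is needed because Protocol 3.5.5 specifies only the telephone contact for failures, although it also asks all participants to continue the daily questionnaire.
3. **Accounting.** Base the SAP 3.3.3 table on all randomized participants, as Protocol 9.3.4 says.
4. **Minor.** SAP 3.1.4.7 says that time to rescue runs from randomization, but its formula uses the date of successful insertion. Reconcile the two. SAP 3.1.1 needs no change for this purpose, since it counts from the date of administration and sets no success condition.

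**Cost.** Protocol and SAP text, one extra AE table and one extra sensitivity analysis. Primary power is unchanged, because the primary set stays the same.

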3.2.2 Intent-to-Treat (ITT) Analysis Set

ITT analysis set: all randomized participants who successfully received the study treatment (LYR-210 or control) on Day 1. This is the primary analysis set for assessment of efficacy. The primary analysis will be conducted for ITT Analysis Set without nasal polyp while the remaining efficacy analyses will be conducted for ITT Analysis Set. Participants will be analyzed according to the treatment they were assigned to at randomization.

3.2.3 Per-Protocol (PP) Analysis Set

PP analysis set: all randomized participants who successfully received the study treatment on Day 1, have specific post-Day 1 assessments, and are without any matrix dislodgement before Week 13 or important protocol deviations that might affect the accuracy and/or reliability of efficacy assessments.

